#### *Routine ART initiation procedures (both arms)*

All ART care is provided free to clients as mandated by MoH. All diagnosed HIV-positive individuals who report to clinic reception are registered in the EMRS (ART registrants) and initiate ART same day (ART initiates). All new registrants receive augmented adherence counseling as part of the ART initiation visit. New ART patient visits are scheduled monthly during the first six months on ART and every two or three months thereafter if the patient is stable and adherent to therapy. Routine VL testing occurs at initiation and annually, thereafter. Clinic visits, side effects

and dispensed drugs are captured in EMRS in real-time by clinic staff. LH and MPC follow all MoH protocols based on WHO guidelines [74] including standard indicator reporting: ART outcomes (dead; transferred; alive on ART; stopped ART; never started ART; and LTFU), VL, and adherence [75].

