## Executive Summary

In sub-Saharan Africa (SSA), retention of HIV-infection people in antiretroviral therapy (ART) care is an increasing challenge. With only 67% retained on ART in SSA, over 7.5 million people are out of care, threatening both individual health and HIV epidemic control. With significant healthcare system constraints and formidable healthcare worker (HCW) shortages, ART services in SSA struggle to meet ambitious global targets of 90% retained in care. In research settings, text-based mHealth innovations show promise to increase ART retention and, therefore, reduce viral load (VL). However, few mHealth innovations have been tested or proven effective in real-world settings with severe human and financial resource constraints. mHealth innovations that successfully retain more patients on ART within large-volume public ART clinics in SSA are urgently needed. Lighthouse Trust (LT), the largest public provider of ART in Malawi, operates two large clinics in Lilongwe with the Malawi Ministry of Health (MoH), Lighthouse Clinic (LH) and Martin Preuss Center (MPC), with a combined 35,000 ART patients. 12-month retention at Lighthouse is 67%, below the 90% global target for epidemic control. Both clinics employ a real-time electronic medical records system (EMRS) and implement a resource-intensive patient retention program, Back to Care (B2C). B2C aims to trace patients who miss ART visits by  $\geq 14$  days. MPC has over 7800 monthly ART visits, and more than 10% of clients are B2C-eligible. B2C demand, coupled with HCW constraints, results in tracing of only 33% of target clients. Lack of, or delayed, tracing reduces ART retention. Moreover, over 50% of traced B2C clients are found on ART, 60% of whom had transferred, demonstrating significant unnecessary tracing. Poor data quality reduces B2C effectiveness. Therefore, LT and the University of Washington's International Training and Education Center for Health (I-TECH), and Medic Mobile, implemented an innovative, proactive, patient retention system using two-way texting (2wT) between new ART patients and staff. A previous study (#20/06/2565 Two-way Texting (2wT) to Improve Patient Retention While Reducing the Healthcare Workload in High-Burden Public HIV Clinics in Urban Lilongwe) suggested that 2wT improved retention, resolved potential retention issues before they occurred and improved data quality (e.g. identifying transfers), potentially reducing B2C workload. MoH requested a randomized control trial to create more rigorous evidence of 2wT impact. Therefore, with 2wT fully operational, we now implement a pragmatic randomized control at LT trial using routine 2wT teams. The pragmatic RCT will test the existing 2wT intervention to provide adherence support for, and visit-focused communication with, new ART initiates at both LH and MPC clinics, comparing 6-month retention (ART outcomes, visit adherence, VL) and B2C referrals among two groups of new ART clients: 2wT-supported (intervention) and routine B2C (control). With this rigorous evidence, we set the stage for national or regional 2wT scale-up.

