## Methods:

### *Overall approach*

**Overview** (See key activities and study timing in Appendix 7, Table 2): Building on the previous 2wT study, this study conducts an RCT for strengthened evidence generation. Over 12 months, we will conduct an RCT in both MPC and LH to prove if 2WT increases 6-month retention (clinic visits, ART outcomes, VL) and reduces workload in both MPC and LH clinics. 6-month outcomes are used as the timeframe is short due to funding constraints. For the RCT, no changes are required in the 2wT software beyond a field for randomization arm. No changes to the educational materials nor to the implementation are needed. The RCT will enroll 410 participants, randomized 1:1 2wT and control. At 6 months, all participants will receive 2wT and continue with 2wT in routine retention activities. The RCT will provide rigorous evidence and generate lessons in direct response to the request of the MoH DHA for more evidence of 2wT impact.

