## *Study outcomes*

Primary retention outcomes: 1) Proportion of patients retained in care at 6-months; (2) visit attendance; and 3) VL (suppressed = HIV RNA < 400 copies). Primary workload outcome is cumulative B2C referrals at 6 months. Secondary outcomes include: Text response rates, #visit date change requests, #ART outcomes updated, % of failed messages, client contact number updates, % referral of true LTFU for tracing, and B2C tracing outcomes (transfer, stop, alive, etc.).

Table: Outcomes	Definition	Source	Phase	
Individual level (Reach and Effectiveness):			R21	R33
Retention outcomes				
Retention	6-month ART retention (alive on ART or client report of transferred care)	EMRS	X	X
ART visit adherence	% of visits attended		X	X
Viral load	% suppressed (HIV RNA <400 copies)			
Workload outcome:				
Healthcare workload	# cumulative B2C referrals at 6 months; time spent on 2WT and B2C	Time-motion, EMRS, 2WT database	X	X

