#### **Data abstracted from EMRS:**

- Basic demographic data such as name and age, WHO stage
- Routine ART visit dates, viral load, adherence, ART outcomes

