#### **Supplemental, study-specific data includes:**

- Enrollment form: confirmation of study consent, enrollment date, phone company, cell number
- Non-routine data in 2WT database: client messages exchanged with 2WT staff, message failures, visit date changes, ART outcomes completed.

Data for program retention (clinic visits, ART outcomes, VL), will be extracted from routine EMRS for both 2WT and comparison clients. B2C referrals and outcomes will come 2WT database (intervention) and from the routine B2C database (comparison). Process data from the 2wT database includes all other data for secondary outcomes.

Data collection timing: prospective for new initiates in 2WT and retrospective comparison without 2WT.

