### *Data analysis*

#### *Retention:*

Descriptive statistics will be performed to explore the patients' characteristics at ART initiation using means or medians for continuous variables and proportions for categorical variables. Chi-square test and Kruskal-Wallis tests will be used to compare baseline characteristics. The proportion of patients retained in ART care (or known transferred in care) at 6 and 12 months post-ART initiation between groups using chi-square test will be compared, reporting relative risks and 95% confidence intervals (CIs). Time to event analysis will explore retention curves between groups in the first year of ART. T-test will compare the mean proportion of attended ART visits between groups. VL suppression (HIV RNA < 400 copies) at 12 months post-ART initiation will be compared between groups using chi-square test, reporting relative risks and 95% CIs. Multivariate logistic regression models (12-month retention v not) will quantify the magnitude of retention difference between groups, adjusting for any potential confounders (age, sex, WHO stage at ART initiation, etc.). Statistical analysis: B2C referrals (workload) outcomes: T-test will compare the cumulative number of B2C referrals between groups. A multivariate linear regression model will further quantify the effect of intervention on referrals, adjusting for potential confounders. For the RCT, the above outcomes will be measured and compared between arms at 6 months.

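### Viral load suppression at 6 months is a primary RCT outcome, but the routine test schedule gives an on-treatment result in the randomized period only to those enrolled at or near 6 months on ART

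*Combined protocol and SAP*

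**What the plan says.** Study outcomes gives VL primary status: "Primary retention outcomes: 1) Proportion of patients retained in care at 6-months; (2) visit attendance; and 3) VL", with suppression defined as HIV RNA below 400 copies.

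The time point for the RCT is 6 months. The Executive Summary describes the trial as "comparing 6-month retention (ART outcomes, visit adherence, VL) and B2C referrals among two groups of new ART clients", and Overall approach also names VL within 6-month retention. Data analysis (Retention) has general text that sets a later time: "VL suppression (HIV RNA < 400 copies) at 12 months post-ART initiation will be compared between groups using chi-square test". It closes with a sentence specific to this trial: "For the RCT, the above outcomes will be measured and compared between arms at 6 months".

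The source is routine records. The list of items abstracted from the EMRS includes viral load, and Data sources adds: "Data for program retention (clinic visits, ART outcomes, VL), will be extracted from routine EMRS for both 2WT and comparison clients". The sections available describe no study-specific VL draw, no window around the time point and no rule for missing VL.

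On when routine VL is done, Routine ART initiation procedures (both arms) says: "Routine VL testing occurs at initiation and annually, thereafter".

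Two other provisions matter. Participant eligibility admits people from ART registration up to 6 months after initiation. Study design and item 11 of Study procedures give 2wT to the control arm once 6 months have passed.

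**The concern.** A primary comparison needs outcome data collected while the arms still differ. Here the outcome comes from a routine schedule with one test at ART start, which is a baseline value, and the next a year later. The randomized contrast lasts only 6 months and mostly closes before that second test is due.

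At analysis the team would have to choose, without a plan, among three sources: baseline values, a small group of late enrollees plus whatever unscheduled tests are in the record, or month-12 tests taken after controls had started 2wT. None of these is the stated comparison of 2wT with routine B2C on 6-month suppression in the randomized population.

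The problem is confined to VL. The objectives and the sample size concern retention and workload.

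**Working it through.** The plan gives no VL suppression rate, precision or power, so there is no VL figure to reproduce. The check is one of timing.

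**Inputs from the protocol**
- Scheduled VL at months 0 and 12 on ART (Routine ART initiation procedures).
- Enrollment at m months on ART, 0 ≤ m ≤ 6 (Participant eligibility).
- Randomized contrast of 6 months from enrollment, then 2wT for all (Study design).
- 410 participants, 205 per arm, with up to 500 enrolled (Sample size calculation).

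**Assumptions, because the protocol does not give these**
- p0 = share enrolled at initiation. The rest are spread evenly over 0 to 6 months.
- t = how many months before month 12 the annual test may be drawn.
- Unscheduled tests are not counted.

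**Step 1. Randomized window on the ART clock: m to m+6**

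| Enrolled at month | Window on ART | Control time on 2wT by a month-12 test (6−m) |
|---|---|---|
| 0 | 0–6 | 6 months |
| 1 | 1–7 | 5 |
| 2 | 2–8 | 4 |
| 3 | 3–9 | 3 |
| 4 | 4–10 | 2 |
| 5 | 5–11 | 1 |
| 6 | 6–12 | 0 |

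A test at exactly month 12 falls in the window only when m = 6.

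**Step 2. If 6 months is counted from ART start**, as in Specific objectives, the window is months 0 to 6. Drawn even 2 months early, the annual test comes at month 10. The share with a scheduled on-treatment VL is 0%.

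**Step 3. If 6 months is counted from enrollment**, a test at month 12−t is in the window when m ≥ 6−t. The share is (1−p0) × t/6.
- p0 = 0.9, t = 0.5: 0.1 × 0.5/6 = 0.83%, about 3 of 410.
- p0 = 0.7, t = 1: 0.3 × 1/6 = 5.0%, about 21.
- p0 = 0.5, t = 2: 0.5 × 2/6 = 16.7%, about 68 (34 per arm).
- p0 = 0, t = 0.5: 0.5/6 = 8.3%, about 34 (17 per arm).
- p0 = 0, t = 2: 2/6 = 33.3%, about 137 (68 per arm), or 167 of 500 (83 per arm).
- p0 = 0, t = 3: 3/6 = 50%, 205 (about 102 per arm).

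**Step 4. Precision.** The 95% CI half-width for a difference in proportions is 1.96 × √(2p(1−p)/n), with n per arm and p the suppression rate (assumed 80% or 90%).

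| n per arm | p = 80% | p = 90% |
|---|---|---|
| 34 | 19.0 points | 14.3 points |
| 68 | 13.4 | 10.1 |
| 83 | 12.2 | 9.1 |
| 102 | 11.0 | 8.2 |
| 205 (everyone tested) | 7.7 | 5.8 |

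These treat everyone with a test due in the window as retained and tested, so actual intervals would be wider.

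**Step 5. If the 12-month text were used instead**, mean control exposure to 2wT before the test is p0 × (6−t) + (1−p0) × (6−t)²/12.
- p0 = 0.5, t = 2: 0.5 × 4 + 0.5 × 16/12 = 2.67 months.
- p0 = 0.9, t = 0.5: 0.9 × 5.5 + 0.1 × 30.25/12 = 5.20 months.
- p0 = 0: 16/12 = 1.3 months at t = 2, and 30.25/12 = 2.5 months at t = 0.5.

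**The case against.** The best defence is that Data analysis gives VL its own time point, 12 months after ART initiation, and that Participant eligibility says the entry rule lets all outcome data be collected by 12 months. A comparison by randomized arm at that point is still randomized. A rule for untested people could deal with selection, and the result could be kept as a secondary analysis.

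Part of this stands: a 12-month comparison by arm would be legitimate if labelled for what it is. It does not rescue the stated outcome. The last sentence of the same section sets 6 months for the RCT. The eligibility sentence does not bring anyone's test forward to before crossover. By month 12, controls enrolled before month 6 have had 2wT, so the question becomes immediate versus deferred 2wT. VL would also exist only for people still in care and tested, and staying in care is what the intervention is meant to change.

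It is also fair to say that VL is in neither the objectives nor the sample size, so the main conclusions survive. That limits the damage, but VL is still listed as primary.

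Finally, the shares depend on assumptions. With no one enrolled at initiation and tests drawn 3 months early, half the sample would have a test in the window. Unscheduled tests may also be in the EMRS. The plan defines neither source, and recruitment is built mainly around initiation counseling. The appendices, including the timing table cited in Overall approach, were not available for this check, so a VL procedure stated only there cannot be ruled out.

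**Conclusion.** The concern holds. On the plan's own schedule and data source, 6-month VL suppression cannot be compared between 2wT and routine B2C in the randomized population as a whole. Counted from ART start, no participant has a scheduled on-treatment VL. Counted from enrollment, only those who join at or near 6 months on ART do.

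The most plausible range is 0.8% to 16.7% of 410, given 50% to 90% enrolled at initiation and tests drawn 0.5 to 2 months early. It rises to 33.3% over the same range of early draws if nobody enrols at initiation. These shares rest on an enrollment mix and a draw window that the documents do not state. The timing conflict itself needs none of these assumptions.

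This should be corrected, because following the plan as written leaves a named primary outcome without scheduled data for most participants. Conclusions on retention and workload are not affected.

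**What to change.** 1. Reconcile Overall approach, Study outcomes, Routine ART initiation procedures, Data sources and Data analysis so that they agree on the VL time point and its source.
2. Remove 6-month VL suppression from the RCT's primary outcomes, and leave the other listed outcomes as they are.
3. Report VL found in the EMRS descriptively by randomized arm, giving the number tested, the number not tested with the reason (not yet due, out of care, transferred), and time on ART at the test.
4. Label any 12-month value as post-crossover: immediate versus deferred 2wT among those tested.

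The cost is a protocol amendment with ethics-committee and trial-registry updates. The registry record was not seen, so its wording needs checking. No new data collection or extra testing is required. The trial gives up a primary VL claim that the scheduled data could not have supported.

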### *Study procedures*

#### Processes between 2wT and routine Back to Care (B2C)

Specific Activities	Increased retention via Two-way texting	
	Control	2wT
PROACTIVE ART RETENTION		
Automated blast weekly adherence SMS for new ART initiates		X
2wT hybrid visit reminders 3 and 1 day before visits		X
2wT interaction/calls for those respond “no” to visits		X
EARLY ACTIONS TO REDUCE LTFU AMONG 2WT ENROLLEES		
2wT hybrid visit reminders at 5, 8, 11 days post visit		X
Updating of client reported ART outcomes (transfers, etc.) <14 days		X
If no client visit/contact, day 14 alert created: refer to B2C		X
B2C phone and home tracing of patients presumed LTFU	X	X

#### *Control/comparison group (Routine Back to Care (B2C)):*

All patients are eligible for B2C. Patients with any ART drug dispensing record (including initiation) who missed a scheduled appointment by 14 days or more are identified using the EMRS and considered LTFU. A team of B2C tracers manually verifies the LTFU list to rule out EMRS data errors and creates a paper-based B2C tracing list. Then, patients with completed locator forms are first traced by phone (SMS or call) up to five phone attempts and/or then up to three home visit attempts. The EMRS at ART patient registration is used daily to determine if/when a client returns to care and to stop B2C client follow-up for that specific event/month. For all patients reached, B2C interviews clients to ascertain ART outcomes and records data on paper B2C forms; data clerks enter it into the EMRS.

#### *2WT (intervention):*

All new ART registrants who fill locator forms will be asked to consent to 2WT; those who enroll will receive an enrollment confirmation text, additional texting information, and response instruction at initiation. ART initiates who fail to bring their phone at their first visit or otherwise decide to participate after the initiation visit will be eligible to join the study at any visit within the first 6 months on ART. They will also be asked to consent to 2WT; those who enroll will receive an enrollment confirmation text, additional texting information, and response instruction at enrollment. 2wT paper clients files will be marked to alert reception of participation. Then, 2WT data clerk will manually enter client unique ID, client phone number and scheduled visit dates into 2WT system. Successful SMS receipt is verified by 2WT’s system; failed SMS creates a system report. Based on these inputs, the 2WT system will automatically send varying, weekly adherence

support texts and visit reminders (3 and 1 day before) for 12 months, with opt-out at any time. Clients will be asked to respond to visit reminder messages with a “1=will attend” or “0=no.” A “yes” will trigger, “See you soon!” A “no” will trigger hybrid automated and interactive SMS follow-up where clients can request an appointment date change, report transfers, note other outcome, or request a call. These modifiable, scripted texts between 2wT staff and the client will complete ART outcome data (transfer, stop, etc.) or determine the next steps (**Figure 2** for mock-up).

6. If a 2WT ART client responds they will not attend a visit, a 2WT staff will exchange modifiable, scripted texts with the client to determine to change visit date, record transfer or other. Multiple responses and free text are acceptable. Regardless of response, the 2wT will enter into interactive texting with the client.
7. No client has to respond to messages
8. Any 2wT client, as per routine care who does not respond and does not attend any visit by >14 days will be referred to routine B2C

9. Data from the 2wT toolkit, participating clients, and ART forms will be reconciled by the Lighthouse study team as per routine monthly reporting requirements. Data on all visits will be entered into the online 2wT toolkit database.
10. Brief, self-administered, mixed-method surveys on 2WT usability (Appendix 3: usability survey with clients) will be implemented at ART visits at 3- and 6-months with a subset of 100 2WT clients (50 at 3 months/50 at 6 months) to gauge client acceptability, self-efficacy, perceived benefits, and barriers to 2WT for intervention improvement. Clients may refuse to participate in these surveys and will be replaced to reach 100.
11. At 6 months, RCT participants who were randomized to routine retention will be enrolled into 2wT

### *Data sources*

During the course of the study, in both year 1 and 2, study team members will review existing paper-based records at the site with identified patient data, including paper ART visit forms for purposes of data quality assurance. Data will be collected across two objectives: data abstractions from participants'routine ART data in the electronic medical records system (EMRS) as well as supplemental information from the 2WT database. EMRS data is routine data. 2WT system data entry and forms will be checked for completeness and correctness on a weekly basis. Data for analysis will be abstracted only from the study database.

#### **Data abstracted from EMRS:**

- Basic demographic data such as name and age, WHO stage
- Routine ART visit dates, viral load, adherence, ART outcomes

#### **Supplemental, study-specific data includes:**

- Enrollment form: confirmation of study consent, enrollment date, phone company, cell number
- Non-routine data in 2WT database: client messages exchanged with 2WT staff, message failures, visit date changes, ART outcomes completed.

Data for program retention (clinic visits, ART outcomes, VL), will be extracted from routine EMRS for both 2WT and comparison clients. B2C referrals and outcomes will come 2WT database (intervention) and from the routine B2C database (comparison). Process data from the 2wT database includes all other data for secondary outcomes.

Data collection timing: prospective for new initiates in 2WT and retrospective comparison without 2WT.

### *Data analysis*

#### *Retention:*

Descriptive statistics will be performed to explore the patients' characteristics at ART initiation using means or medians for continuous variables and proportions for categorical variables. Chi-square test and Kruskal-Wallis tests will be used to compare baseline characteristics. The proportion of patients retained in ART care (or known transferred in care) at 6 and 12 months post-ART initiation between groups using chi-square test will be compared, reporting relative risks and 95% confidence intervals (CIs). Time to event analysis will explore retention curves between groups in the first year of ART. T-test will compare the mean proportion of attended ART visits between groups. VL suppression (HIV RNA < 400 copies) at 12 months post-ART initiation will be compared between groups using chi-square test, reporting relative risks and 95% CIs. Multivariate logistic regression models (12-month retention v not) will quantify the magnitude of retention difference between groups, adjusting for any potential confounders (age, sex, WHO stage at ART initiation, etc.). Statistical analysis: B2C referrals (workload) outcomes: T-test will compare the cumulative number of B2C referrals between groups. A multivariate linear regression model will further quantify the effect of intervention on referrals, adjusting for potential confounders. For the RCT, the above outcomes will be measured and compared between arms at 6 months.

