### *Specific objectives*

1. To determine how much 2-way, visit reminder texting between the Lighthouse clinic and Lighthouse patients can increase new ART client retention and reduce the tracing workload within the first 6 months on ART

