### *Study design*

[figure not shown]
In this current pragmatic RCT study, we randomize eligible 2wT patients who wish to opt-into 2wT, allocating them 1:1 to 2wT and routine Back to Care (B2C) retention efforts. For 6 months, each participant will receive the assigned intervention (2wT or control). At 6 months post enrollment, all RCT participants will receive 2wT and continue with 2wT support as part of routine LT retention activities. We will enroll at both LH and MPC, using results to provide the MoH with data needed to consider 2wT for scale-up.

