## *Sample size calculation*

Supposing a two-arm prospective study with 3-4 months recruitment period and 6 months follow-up. Assume the hazard for the control group is a constant risk over time at 0.2 (20%). To achieve 80% power to detect a hazard ratio of 0.41 in the exposed group by using a two-sided 0.05-level log-rank test, the required sample size per arm is 197. With an estimated dropout of 10%, 410 (205 per arm) will be needed, and up to 500 will be enrolled, total, to allow for buffer and withdrawal of those with lack of SMS confirmation receipt (documented).).

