## *Participant eligibility*

The intervention will be offered to all new ART registrants and new ART initiates (clients who initiated ART in the last 6 months) at MPC and LH aged 18 years and above with mobile phones. This allows for collection of all outcome data by 12 months. 2WT-specific eligibility criteria for all clients are: 1) New ART registrants (Initial screening visit for ART initiation) OR new ART initiate (within 6 months of initiating ART); 2)  $\geq 18$  years; 3) possession of own phone at enrollment; 4) willing to receive/send SMS; 5) informed consent; 6) receives confirmed 2WT enrollment text to verify enrollment number; and 7) initiates ART. Those without cell phones will

be excluded. As phone sharing is common, informed 2WT-specific consent will ascertain whether eligible clients have consistent access to send and receive messages. Patients will see example text context that will not contain HIV- or clinic-based information to reduce risk of disclosure; these steps have been used in similar SMS-based studies [72, 73]. 2WT cannot control message content sent by clients. Study-eligible clients will be automatically enrolled into 2wT messages with confirmed ART dispensing. Consenting 2wT enrollees who do not initiate ART will not be sent messages.

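### The RCT's 6-month outcomes have no agreed time origin: the objective and the retention analysis count from ART start, the assigned arm from enrolment up to 6 months later

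*Combined protocol and SAP*

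**What the plan says.** Two origins appear in the current text.

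- **ART start.** The single specific objective is to increase retention and "reduce the tracing workload within the first 6 months on ART". Data analysis (Retention) compares "The proportion of patients retained in ART care (or known transferred in care) at 6 and 12 months post-ART initiation between groups", draws retention curves over the first year of ART, and tests viral load suppression "at 12 months post-ART initiation will be compared between groups using chi-square test".
- **Enrolment.** Study design gives each participant the assigned arm for 6 months, then: "At 6 months post enrollment, all RCT participants will receive 2wT".

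The two dates need not coincide. Participant eligibility admits "New ART registrants (Initial screening visit for ART initiation) OR new ART initiate (within 6 months of initiating ART"), and the 2WT (intervention) section lets clients join at any visit in that period.

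The Retention section closes with "For the RCT, the above outcomes will be measured and compared between arms at 6 months", without saying from when. Study outcomes, Overall approach and item 11 of the numbered participant procedures also give 6 months with no origin.

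**The concern.** A randomised comparison should start at randomisation and stop before the control arm receives the intervention. The clock written in the retention analysis does neither for a client who joins after starting ART. The trial is open-label, so an origin left unstated for the primary retention count could be chosen after results are known.

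On the ART-initiation clock, three things go wrong for late joiners:

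- They contribute less than 6 months of randomised follow-up, and none if they join at month 6.
- Losses later in their assigned period are not counted.
- Visits and B2C referrals that happened before randomisation could be counted.

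Viral load raises a separate question. It is a primary retention outcome, but Routine ART initiation procedures schedules testing only at initiation and then annually.

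**Working it through.** **The plan's own figure.** Sample size calculation gives 197 per arm for a hazard of 0.2, a hazard ratio of 0.41 and 80% power. The hazard has no time unit, so 197 can be neither confirmed nor refuted. The Schoenfeld formula needs 4 × (1.960 + 0.842)² / (ln 0.41)² = 39.5 events. With a fixed 6-month follow-up:

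- 0.2 per 6 months: 39.5 / (0.1813 + 0.0787) gives 152 per arm.
- 0.2 per year: 39.5 / (0.0952 + 0.0402) gives 292 per arm.

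The finding does not depend on 197, but both hazard readings are carried below.

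**One client on two clocks.** A client randomised at month 4 on ART and lost at month 8 is retained at 6 months post-ART and lost at 6 months post-enrolment. In general, joining at month k leaves 6 − k randomised months on the ART clock, against 6 on the enrolment clock.

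**Illustration of dilution on the ART clock.** From the plan: hazard 0.2, hazard ratio 0.41, 205 per arm, 10% dropout, chi-square test. Assumed: constant hazard, late joiners spread uniformly over months 0 to 6, and a late share s, which the documents do not give.

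Let H be the cumulative hazard over 6 months.

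- Loss if joined at initiation: 1 − exp(−H).
- Loss if joined late: 1 − (1 − exp(−H))/H.
- Arm total: the two weighted by 1 − s and s.
- Power = Φ{[|pc − pt|√n − 1.96√(2p̄(1 − p̄))] / √[pc(1 − pc) + pt(1 − pt)]}.

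With 0.2 per 6 months, H is 0.2 in control and 0.2 × 0.41 = 0.082 in 2wT. Loss is 0.1813 and 0.0787 if joined at initiation, and 0.0937 and 0.0399 if joined late. At s = 25%:

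- Control: 0.75 × 0.1813 + 0.25 × 0.0937 = 0.159.
- 2wT: 0.75 × 0.0787 + 0.25 × 0.0399 = 0.069.
- Relative risk of retention: 0.931/0.841 = 1.107.

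| Late share | Loss, control / 2wT | Risk difference (points) | Relative risk of retention | Power, 205 per arm | Power, 185 per arm (205 × 0.9) |
|---|---|---|---|---|---|
| 0% | 0.181 / 0.079 | 10.3 | 1.125 | 87% | 84% |
| 25% | 0.159 / 0.069 | 9.0 | 1.107 | 82% | 78% |
| 50% | 0.138 / 0.059 | 7.8 | 1.091 | 76% | 72% |

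If 0.2 is a yearly hazard (H = 0.1 and 0.041), power at 205 per arm is 60%, 54% and 48% at 0%, 25% and 50% late.

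**Viral load.** The first annual test falls at about month 12 on ART. For a client randomised at month k (0 to 6) that is 12 − k, or 6 to 12 months after randomisation, at or after the switch of all participants to 2wT.

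**The case against.** The strongest reply is that the plan already points to enrolment. The closing sentence of the Retention section takes the RCT away from the 12-month wording, which may be carried over from the earlier study. The sample size assumes "Supposing a two-arm prospective study with 3-4 months recruitment period and 6 months follow-up", and Participant eligibility adds "This allows for collection of all outcome data by 12 months", which fits 6 months to join plus 6 months of follow-up. Study design fixes the switch by enrolment.

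Much of this stands. A reader might infer that the RCT will be analysed at 12 months, with controls already on 2wT; the closing sentence does not support that. But that sentence changes the horizon, not the origin, and the outcomes it refers back to include retention at 6 months post-ART initiation. The other passages favour enrolment without stating it, and the objective still says otherwise.

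It can also be said that few will join late, since recruitment centres on initiation counselling, and for anyone who enrols and starts ART the same day the clocks coincide. That may be so. The figure of over 92% starting ART the same day describes registrants, not when RCT participants enrol. Nor can a late share be forecast from the clinics' quarterly ART starts, because those already on ART need not be as likely to be recruited as new starters.

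**Conclusion.** The conflict is real and should be fixed. Read literally, the retention analysis shortens the randomised comparison for late joiners. For retention the expected effect is dilution. The amount is unknown, and the power figures are illustrations that depend on the late share, the hazard unit and dropout.

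Three stronger readings are not supported:

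- **That the trial falls below 80% power because of the clock.** At 25% late, power is 82% with 205 per arm and 78% with 185. If the hazard is yearly, power is about 60% with no late joiners at all, and the clock is then secondary.
- **That no outcome can be biased between arms.** Data sources takes B2C referrals from the 2WT database for intervention and the routine B2C database for comparison, so referrals before randomisation could enter unequally. Bias in the workload outcome cannot be excluded.
- **That viral load fits no clock.** Twelve months post-ART matches the annual test. The mismatch is between routine testing and a 6-month RCT endpoint, and it exists under either origin.

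**What to change.** In Study outcomes and Data analysis:

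- Define time zero as the date of randomisation for RCT retention, visit attendance, B2C referrals and retention curves.
- Count only visits and referrals after randomisation, and end the randomised comparison at 6 months post-randomisation, before controls start 2wT.
- State how participants randomised before ART dispensing are handled, since registrants can be randomised before they start ART.
- State that the 12-month and first-year analyses are not part of the RCT comparison.
- Align the specific objective, and give the origin in item 11 of the participant procedures.

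For viral load, reconcile Study outcomes, Routine ART initiation procedures and Data analysis before data are seen. Either fix a window around 6 months post-randomisation and report the number of results per arm, or state now that viral load is outside the 6-month randomised comparison. The choice should not wait on how many results turn up. Adjustment for months on ART at randomisation is optional.

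Cost: no new data, since enrolment and visit dates are already collected. The objective is reworded, and for late joiners the estimate extends up to month 12 on ART.
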